Arteriotomy	Iliac artery occlusion	Retinal vascular thrombosis
Arteriovenous fistula occlusion	Iliac vein occlusion	Retinal vein occlusion
Arteriovenous fistula thrombosis	Implant site thrombosis	Retinal vein thrombosis
Arteriovenous graft thrombosis	Incision site vessel occlusion	Revascularisation procedure
Artificial blood vessel occlusion	Infarction	Shunt occlusion
Aseptic cavernous sinus thrombosis	Inferior vena cava syndrome	Shunt thrombosis
Atherectomy	Inferior vena caval occlusion	SI QIII TIII pattern
Atherosclerotic plaque rupture	Infusion site thrombosis	Silent myocardial infarction
Atrial appendage closure	Injection site thrombosis	Spinal artery embolism
Atrial appendage resection	Inner ear infarction	Spinal artery thrombosis
Atrial thrombosis	Instillation site thrombosis	Spinal cord infarction
Autoimmune heparin-induced thrombocytopenia	Internal capsule infarction	Spinal stroke
Axillary vein thrombosis	Intestinal infarction	Splenic artery thrombosis
Basal ganglia infarction	Intra-aortic balloon placement	Splenic embolism
Basal ganglia stroke	Intracardiac mass	Splenic infarction
Basilar artery occlusion	Intracardiac thrombus	Splenic thrombosis
Basilar artery thrombosis	Intraoperative cerebral artery occlusion	Splenic vein occlusion
Blindness transient	Ischaemic cerebral infarction	Splenic vein thrombosis
Bone infarction	Ischaemic stroke	Stoma site thrombosis
Brachiocephalic artery occlusion	Jugular vein embolism	Stress cardiomyopathy
Brachiocephalic vein occlusion	Jugular vein occlusion	Stroke in evolution
Brachiocephalic vein thrombosis	Jugular vein thrombosis	Strokectomy
Brain stem embolism	Lacunar infarction	Subclavian artery embolism
Brain stem infarction	Lambli's excrescences	Subclavian artery occlusion
Brain stem stroke	Left atrial appendage closure implant	Subclavian artery thrombosis
Brain stem thrombosis	Leriche syndrome	Subclavian vein occlusion

Document: [REDACTED]

Author: [REDACTED]

Version Number: 2.5

Version Date: 18Feb2022

Template No.: [REDACTED]

Reference: CS_WI_BS005

Effective Date: 02Dec2019

Budd-Chiari syndrome	Mahler sign	Subclavian vein thrombosis
Capsular warning syndrome	May-Thurner syndrome	Superficial vein thrombosis
Cardiac ventricular thrombosis	Medical device site thrombosis	Superior sagittal sinus thrombosis
Carotid angioplasty	Mesenteric arterial occlusion	Superior vena cava occlusion
Carotid arterial embolus	Mesenteric arteriosclerosis	Superior vena cava syndrome
Carotid artery bypass	Mesenteric artery embolism	Surgical vascular shunt
Carotid artery occlusion	Mesenteric artery stenosis	Testicular infarction
Carotid artery stent insertion	Mesenteric artery stent insertion	Thalamic infarction
Carotid artery thrombosis	Mesenteric artery thrombosis	Thrombectomy
Carotid endarterectomy	Mesenteric vascular insufficiency	Thromboangiitis obliterans
Catheter directed thrombolysis	Mesenteric vascular occlusion	Thromboembolectomy
Catheter site thrombosis	Mesenteric vein thrombosis	Thrombolysis
Catheterisation venous	Mesenteric venous occlusion	Thrombophlebitis
Cavernous sinus thrombosis	Microembolism	Thrombophlebitis migrans
Central venous catheterisation	Monoparesis	Thrombophlebitis neonatal
Cerebellar artery occlusion	Monoplegia	Thrombosed varicose vein
Cerebellar artery thrombosis	Muscle infarction	Thrombosis
Cerebellar embolism	Myocardial infarction	Thrombosis corpora cavernosa
Cerebellar infarction	Myocardial necrosis	Thrombosis in device
Cerebral artery embolism	Obstetrical pulmonary embolism	Thrombosis mesenteric vessel
Cerebral artery occlusion	Obstructive shock	Thrombosis prophylaxis
Cerebral artery stent insertion	Ophthalmic artery occlusion	Thrombosis with thrombocytopenia syndrome
Cerebral artery thrombosis	Ophthalmic artery thrombosis	Thrombotic cerebral infarction
Cerebral congestion	Ophthalmic vein thrombosis	Thrombotic microangiopathy
Cerebral hypoperfusion	Optic nerve infarction	Thrombotic stroke
Cerebral infarction	Ovarian vein thrombosis	Thrombotic thrombocytopenic purpura
Cerebral infarction foetal	Paget-Schroetter syndrome	Thyroid infarction
Cerebral ischaemia	Pancreatic infarction	Transient ischaemic attack
Cerebral microembolism	Papillary muscle infarction	Transverse sinus thrombosis

Document: [REDACTED]

Author: [REDACTED]

Version Number: 2.5

Version Date: 18Feb2022

Template No.: [REDACTED]

Reference: CS_WI_BS005

Effective Date: 02Dec2019

Cerebral microinfarction	Paradoxical embolism	Truncus coeliacus thrombosis
Cerebral septic infarct	Paraneoplastic thrombosis	Tumour embolism
Cerebral thrombosis	Paraparesis	Tumour thrombectomy
Cerebral vascular occlusion	Paraplegia	Tumour thrombosis
Cerebral venous sinus thrombosis	Paresis	Ultrasonic angiogram abnormal
Cerebral venous thrombosis	Pelvic venous thrombosis	Ultrasound Doppler abnormal
Cerebrospinal thrombotic tamponade	Penile artery occlusion	Umbilical cord occlusion
Cerebrovascular accident	Penile vein thrombosis	Umbilical cord thrombosis
Cerebrovascular accident prophylaxis	Percutaneous coronary intervention	Vaccination site thrombosis
Cerebrovascular disorder	Peripheral arterial occlusive disease	Vascular access site thrombosis
Cerebrovascular insufficiency	Peripheral arterial reocclusion	Vascular device occlusion
Cerebrovascular operation	Peripheral artery angioplasty	Vascular graft
Cerebrovascular stenosis	Peripheral artery bypass	Vascular graft occlusion
Choroidal infarction	Peripheral artery occlusion	Vascular graft thrombosis
Coeliac artery occlusion	Peripheral artery stent insertion	Vascular operation
Collateral circulation	Peripheral artery surgery	Vascular pseudoaneurysm thrombosis
Compression garment application	Peripheral artery thrombosis	Vascular stent insertion
Coronary angioplasty	Peripheral embolism	Vascular stent occlusion
Coronary arterial stent insertion	Peripheral endarterectomy	Vascular stent thrombosis
Coronary artery bypass	Peripheral revascularisation	Vasodilation procedure
Coronary artery embolism	Peripheral vein occlusion	Vena cava embolism
Coronary artery occlusion	Peripheral vein thrombus extension	Vena cava filter insertion
Coronary artery reocclusion	Phlebectomy	Vena cava filter removal
Coronary artery surgery	Pituitary infarction	Vena cava thrombosis
Coronary artery thrombosis	Placental infarction	Venogram abnormal
Coronary bypass thrombosis	Pneumatic compression therapy	Venoocclusive disease
Coronary endarterectomy	Popliteal artery entrapment syndrome	Venoocclusive liver disease
Coronary revascularisation	Portal shunt procedure	Venous angioplasty
Coronary vascular graft occlusion	Portal vein cavernous transformation	Venous occlusion

Document: [REDACTED]

Author: [REDACTED]

Version Number: 2.5

Version Date: 18Feb2022

Template No.: [REDACTED]

Reference: CS_WI_BS005

Effective Date: 02Dec2019

Deep vein thrombosis	Portal vein embolism	Venous operation
Deep vein thrombosis postoperative	Portal vein occlusion	Venous recanalisation
Device embolisation	Portal vein thrombosis	Venous repair
Device occlusion	Portosplenomesenteric venous thrombosis	Venous stent insertion
Device related thrombosis	Post procedural myocardial infarction	Venous thrombosis
Diplegia	Post procedural pulmonary embolism	Venous thrombosis in pregnancy
Directional Doppler flow tests abnormal	Post procedural stroke	Venous thrombosis limb
Disseminated intravascular coagulation	Post thrombotic syndrome	Venous thrombosis neonatal
Disseminated intravascular coagulation in newborn	Postinfarction angina	Vertebral artery occlusion
Embolia cutis medicamentosa	Postoperative thrombosis	Vertebral artery thrombosis
Embolic cerebellar infarction	Postpartum thrombosis	Vessel puncture site occlusion
Embolic cerebral infarction	Postpartum venous thrombosis	Vessel puncture site thrombosis
Embolic pneumonia	Precerebral artery embolism	Visceral venous thrombosis
Embolic stroke	Precerebral artery occlusion	Visual acuity reduced transiently
Embolism	Precerebral artery thrombosis	Visual midline shift syndrome
Embolism arterial	Profundaplasty	
	Prosthetic cardiac valve thrombosis	
	Prosthetic vessel implantation	
AESI Category: Hepatic function abnormal		
Acquired antithrombin III deficiency	Gastric variceal ligation	Hypothromboplastinaemia
Acquired factor IX deficiency	Gastric varices	Icterus index increased
Acquired factor V deficiency	Gastric varices haemorrhage	Immune-mediated cholangitis
Acquired factor VIII deficiency	Gastroesophageal variceal haemorrhage prophylaxis	Immune-mediated hepatic disorder
Acquired factor XI deficiency	Graft versus host disease in liver	Immune-mediated hepatitis
Acquired hepatocerebral degeneration	Guanase increased	International normalised ratio abnormal
Acquired protein S deficiency	Haemangioma of liver	International normalised ratio increased
Acute graft versus host disease in liver	Haemorrhagic hepatic cyst	Intestinal varices
Acute hepatic failure	Hepaplastin abnormal	Intestinal varices haemorrhage

Document: [REDACTED]

Author: [REDACTED]

Version Number: 2.5

Version Date: 18Feb2022

Template No.: [REDACTED]

Reference: CS_WI_BS005

Effective Date: 02Dec2019

Acute on chronic liver failure	Hepaplastin decreased	Ischaemic hepatitis
Acute yellow liver atrophy	Hepatectomy	Jaundice
Alanine aminotransferase abnormal	Hepatic adenoma	Jaundice cholestatic
Alanine aminotransferase increased	Hepatic angiosarcoma	Jaundice hepatocellular
Allergic hepatitis	Hepatic artery flow decreased	Kayser-Fleischer ring
Alloimmune hepatitis	Hepatic atrophy	Liver carcinoma ruptured
Ammonia abnormal	Hepatic calcification	Liver dialysis
Ammonia increased	Hepatic cancer	Liver disorder
Anti factor X activity abnormal	Hepatic cancer metastatic	Liver function test abnormal
Anti factor X activity decreased	Hepatic cancer recurrent	Liver function test decreased
Anti factor X activity increased	Hepatic cancer stage I	Liver function test increased
Antithrombin III decreased	Hepatic cancer stage II	Liver induration
Ascites	Hepatic cancer stage III	Liver injury
Aspartate aminotransferase abnormal	Hepatic cancer stage IV	Liver operation
Aspartate aminotransferase increased	Hepatic cirrhosis	Liver palpable
AST/ALT ratio abnormal	Hepatic cyst	Liver scan abnormal
Asterixis	Hepatic cyst ruptured	Liver tenderness
Autoimmune hepatitis	Hepatic cytolysis	Liver transplant
Bacterascites	Hepatic encephalopathy	Lupoid hepatic cirrhosis
Benign hepatic neoplasm	Hepatic encephalopathy prophylaxis	Lupus hepatitis
Benign hepatobiliary neoplasm	Hepatic enzyme abnormal	Magnetic resonance imaging hepatobiliary abnormal
Bile output abnormal	Hepatic enzyme decreased	Magnetic resonance proton density fat fraction measurement
Bile output decreased	Hepatic enzyme increased	Mitochondrial aspartate aminotransferase increased
Biliary ascites	Hepatic failure	Mixed hepatocellular cholangiocarcinoma
Biliary cirrhosis	Hepatic fibrosis	Mixed liver injury
Biliary fibrosis	Hepatic function abnormal	Molar ratio of total branched-chain amino acid to tyrosine
Bilirubin conjugated abnormal	Hepatic haemangioma rupture	Nodular regenerative hyperplasia
Bilirubin conjugated increased	Hepatic hamartoma	Nonalcoholic fatty liver disease

Document: [REDACTED]

Author: [REDACTED]

Version Number:

2.5

Version Date:

18Feb2022

Template No.:

[REDACTED]

Reference: CS_WI_BS005

Effective Date: 02Dec2019

Bilirubin excretion disorder	Hepatic hydrothorax	Non-alcoholic steatohepatitis
Bilirubin urine present	Hepatic hypertrophy	Non-cirrhotic portal hypertension
Biopsy liver abnormal	Hepatic hypoperfusion	Ocular icterus
Blood bilirubin abnormal	Hepatic infiltration eosinophilic	Oedema due to hepatic disease
Blood bilirubin increased	Hepatic lesion	Oesophageal varices haemorrhage
Blood bilirubin unconjugated increased	Hepatic lipoma	Parenteral nutrition associated liver disease
Blood fibrinogen abnormal	Hepatic mass	Perihepatic discomfort
Blood fibrinogen decreased	Hepatic necrosis	Peripancreatic varices
Blood thrombin abnormal	Hepatic neoplasm	Portal fibrosis
Blood thrombin decreased	Hepatic neuroendocrine tumour	Portal hypertension
Blood thromboplastin abnormal	Hepatic pain	Portal hypertensive colopathy
Blood thromboplastin decreased	Hepatic sequestration	Portal hypertensive enteropathy
Bromosulphthalein test abnormal	Hepatic steato-fibrosis	Portal hypertensive gastropathy
Cardiohepatic syndrome	Hepatic steatosis	Portal vein cavernous transformation
Child-Pugh-Turcotte score abnormal	Hepatic vascular resistance increased	Portal vein dilatation
Child-Pugh-Turcotte score increased	Hepatic venous pressure gradient abnormal	Portopulmonary hypertension
Cholaemia	Hepatic venous pressure gradient increased	Primary biliary cholangitis
Cholangiosarcoma	Hepatitis	Protein C decreased
Cholestasis	Hepatitis acute	Protein S abnormal
Cholestatic liver injury	Hepatitis cholestatic	Protein S decreased
Cholestatic pruritus	Hepatitis chronic active	Prothrombin level abnormal
Chronic graft versus host disease in liver	Hepatitis chronic persistent	Prothrombin level decreased
Chronic hepatic failure	Hepatitis fulminant	Prothrombin time abnormal
Chronic hepatitis	Hepatitis toxic	Prothrombin time prolonged
Coagulation factor decreased	Hepatobiliary cancer	Prothrombin time ratio abnormal
Coagulation factor IX level abnormal	Hepatobiliary cancer in situ	Prothrombin time ratio increased
Coagulation factor IX level decreased	Hepatobiliary cyst	Radiation hepatitis
Coagulation factor V level abnormal	Hepatobiliary disease	Regenerative siderotic hepatic nodule
Coagulation factor V level decreased	Hepatobiliary neoplasm	Renal and liver transplant

Document: [REDACTED] x

Author: [REDACTED]

Version Number: 2.5

Version Date: 18Feb2022

Template No.: [REDACTED]

Reference: CS_WI_BS005

Effective Date: 02Dec2019

Coagulation factor VII level abnormal	Hepatobiliary scan abnormal	Retrograde portal vein flow
Coagulation factor VII level decreased	Hepatoblastoma	Reye's syndrome
Coagulation factor X level abnormal	Hepatoblastoma recurrent	Reynold's syndrome
Coagulation factor X level decreased	Hepatocellular carcinoma	Splenic varices
Coma hepatic	Hepatocellular foamy cell syndrome	Splenic varices haemorrhage
Computerised tomogram liver abnormal	Hepatocellular injury	Spontaneous bacterial peritonitis
Congestive hepatopathy	Hepatomegaly	Steatohepatitis
Cryptogenic cirrhosis	Hepatopulmonary syndrome	Steatohepatitis
Diabetic hepatopathy	Hepatorenal failure	Subacute hepatic failure
Drug-induced liver injury	Hepatorenal syndrome	Sugiura procedure
Duodenal varices	Hepatosplenomegaly	Thrombin time abnormal
Flood syndrome	Hepatotoxicity	Thrombin time prolonged
Focal nodular hyperplasia	Hyperammonaemia	Total bile acids increased
Foetor hepaticus	Hyperbilirubinaemia	Transaminases abnormal
Galactose elimination capacity test abnormal	Hypercholia	Transaminases increased
Galactose elimination capacity test decreased	Hyperfibrinolysis	Ultrasound liver abnormal
Gallbladder varices	Hypertransaminasaemia	Urine bilirubin increased
Gamma-glutamyltransferase abnormal	Hypocoagulable state	Varices oesophageal
Gamma-glutamyltransferase increased	Hypofibrinogenaemia	Varicose veins of abdominal wall
Gastric variceal injection	Hypothrombinaemia	White nipple sign
		X-ray hepatobiliary abnormal
AESI Category: Left ventricular ejection fraction decreased		
Acute left ventricular failure	Cardiohepatic syndrome	Hepatojugular reflux
Acute pulmonary oedema	Cardiopulmonary failure	Left ventricular failure
Acute right ventricular failure	Cardiorenal syndrome	Low cardiac output syndrome
Cardiac asthma	Chronic left ventricular failure	Neonatal cardiac failure
Cardiac failure	Chronic right ventricular failure	Obstructive shock
Cardiac failure acute	Congestive hepatopathy	Pulmonary oedema

Document: [REDACTED]

Author: [REDACTED]

Version Number: 2.5

Version Date: 18Feb2022

Template No.: [REDACTED]

Reference: CS_WI_BS005

Effective Date: 02Dec2019

Cardiac failure chronic	Cor pulmonale	Pulmonary oedema neonatal
Cardiac failure congestive	Cor pulmonale acute	Radiation associated cardiac failure
Cardiac failure high output	Cor pulmonale chronic	Right ventricular ejection fraction decreased
Cardiogenic shock	Ejection fraction decreased	Right ventricular failure
		Ventricular failure

APPENDIX 6. CLINICAL LABORATORY PARAMETERS CTCAE CRITERIA

PARAM (SI Unit)	Hypo	Hyper	ATOXGR			
			GRADE 1	GRADE 2	GRADE 3	GRADE 4
		Hemoglobin increased	Increase in >0 - 2 gm/dL above ULN or above baseline if baseline is above ULN	Increase in >2 - 4 gm/dL above ULN or above baseline if baseline is above ULN	Increase in >4 gm/dL above ULN or above baseline if baseline is above ULN	~
Hemoglobin (g/L)	Anemia		Hemoglobin (Hgb) <LLN - 10.0 g/dL; <LLN - 6.2 mmol/L; <LLN - 100 g/L	Hgb <10.0 - 8.0 g/dL; <6.2 - 4.9 mmol/L; <100 - 80g/L	Hgb <8.0 g/dL; <4.9 mmol/L; <80 g/L	~
Platelets (10 ⁹ /L)	Platelet count decreased		<LLN - 75,000/mm ³ ; <LLN - 75.0 x 10e9 /L	<75,000 - 50,000/mm ³ ; <75.0 - 50.0 x 10e9 /L	<50,000 - 25,000/mm ³ ; <50.0 - 25.0 x 10e9 /L	<25,000/mm ³ ; <25.0 x 10e9 /L
Leukocytes (10 ⁹ /L)	White blood cell decreased		<LLN - 3000/mm ³ ; <LLN - 3.0 x 10e9 /L	<3000 - 2000/mm ³ ; <3.0 - 2.0 x 10e9 /L	<2000 - 1000/mm ³ ; <2.0 - 1.0 x 10e9 /L	<1000/mm ³ ; <1.0 x 10e9 /L

Document: [REDACTED]

Author: [REDACTED]

Version Number: 2.5

Version Date: 18Feb2022

Template No.: [REDACTED]

Reference: CS_WI_BS005

Effective Date: 02Dec2019

Neutrophils (10 ⁹ /L)	Neutrophil count decreased		<LLN - 1500/mm ³ ; <LLN - 1.5 x 10 ⁹ /L	<1500 - 1000/mm ³ ; <1.5 - 1.0 x 10 ⁹ /L	<1000 - 500/mm ³ ; <1.0 - 0.5 x 10 ⁹ /L	<500/mm ³ ; <0.5 x 10 ⁹ /L
Lymphocytes (10 ⁹ /L)	Lymphocyte count decreased		<LLN - 800/mm ³ ; <LLN - 0.8 x 10 ⁹ /L	<800 - 500/mm ³ ; <0.8 - 0.5 x 10 ⁹ /L	<500 - 200/mm ³ ; <0.5 - 0.2 x 10 ⁹ /L	<200/mm ³ ; <0.2 x 10 ⁹ /L
		Lymphocyte count increased	~	>4000/mm ³ - 20,000/mm ³	>20,000/mm ³	~
Activated Partial Thromboplastin Time (s)		Activated partial thromboplastin time prolonged	>ULN - 1.5 x ULN	>1.5 - 2.5 x ULN	>2.5 x ULN; bleeding	~
International Normalized Ratio		INR increased	>1.2 - 1.5	>1.5 - 2.5	>2.5	~
Albumin (g/L)	Hypoalbuminemia		<LLN - 3 g/dL; <LLN - 30 g/L	<3 - 2 g/dL; <30 - 20 g/L	<2 g/dL; <20 g/L	~
Glucose (mmol/L)	Hypoglycemia		<LLN - 55 mg/dL; <LLN - 3.0 mmol/L	<55 - 40 mg/dL; <3.0 - 2.2 mmol/L	<40 - 30 mg/dL; <2.2 - 1.7 mmol/L	<30 mg/dL; <1.7 mmol/L
Creatinine (umol/L)		Creatinine increased	>1 - 1.5 x baseline; >ULN - 1.5 x ULN	>1.5 - 3.0 x baseline; >1.5 - 3.0 x ULN	>3.0 baseline; >3.0 - 6.0 x ULN	>6.0 x ULN
Alkaline Phosphatase (IU/L)		Alkaline phosphatase increased	>ULN - 2.5 x ULN	>2.5 - 5.0 x ULN	>5.0 - 20.0 x ULN	>20.0 x ULN

Document: [REDACTED]

Author: [REDACTED]

Version Number:

2.5

Version Date:

18Feb2022

Template No.: [REDACTED]

Reference: CS_WI_BS005

Effective Date: 02Dec2019

Aspartate Aminotransferase (IU/L)		Aspartate aminotransferase increased	>ULN - 3.0 x ULN	>3.0 - 5.0 x ULN	>5.0 - 20.0 x ULN	>20.0 x ULN
Alanine Aminotransferase (IU/L)		Alanine aminotransferase increased	>ULN - 3.0 x ULN	>3.0 - 5.0 x ULN	>5.0 - 20.0 x ULN	>20.0 x ULN
Serum Calcium (mmol/L)		Hypercalcemia	>ULN - 2.9 mmol/L	>2.9 - 3.1 mmol/L	>3.1 - 3.4 mmol/L	>3.4 mmol/L
	Hypocalcemia		<LLN - 2.0 mmol/L	<2.0 - 1.75 mmol/L	<1.75 - 1.5 mmol/L	<1.5 mmol/L
Magnesium (mmol/L)		Hypermagnesemia	>ULN - 3.0 mg/dL; >ULN - 1.23 mmol/L	~	>3.0 - 8.0 mg/dL; >1.23 - 3.30 mmol/L	>8.0 mg/dL; >3.30 mmol/L
	Hypomagnesemia		<LLN - 1.2 mg/dL; <LLN - 0.5 mmol/L	<1.2 - 0.9 mg/dL; <0.5 - 0.4 mmol/L	<0.9 - 0.7 mg/dL; <0.4 - 0.3 mmol/L	<0.7 mg/dL; <0.3 mmol/L
Potassium (mmol/L)		Hyperkalemia	>ULN - 5.5 mmol/L	>5.5 - 6.0 mmol/L	>6.0 - 7.0 mmol/L	>7.0 mmol/L
	Hypokalemia		<LLN - 3.0 mmol/L	~	<3.0 - 2.5 mmol/L	<2.5 mmol/L
Sodium (mmol/L)		Hypernatremia	>ULN - 150 mmol/L	>150 - 155 mmol/L	>155 - 160 mmol/L	>160 mmol/L
	Hyponatremia		<LLN - 130 mmol/L	-	<130 - 120 mmol/L	<120 mmol/L
Total cholesterol (mmol/L)		Cholesterol high	>ULN - 300 mg/dL; >ULN - 7.75 mmol/L	>300 - 400 mg/dL; >7.75 - 10.34 mmol/L	>400 - 500 mg/dL; >10.34 - 12.92 mmol/L	>500 mg/dL; >12.92 mmol/L

Document:

Author:

Template No.:

Effective Date: 02Dec2019

Version Number:

Version Date:

Reference: CS_WI_BS005

2.5

18Feb2022

Bilirubin (umol/L)		Blood bilirubin increased	>ULN - 1.5 x ULN	>1.5 - 3.0 x ULN	>3.0 - 10.0 x ULN	>10.0 x ULN
Triglycerides (mmol/L)		Hypertriglyceridemia	150 mg/dL - 300 mg/dL; 1.71 mmol/L - 3.42 mmol/L	>300 mg/dL - 500 mg/dL; >3.42 mmol/L - 5.7 mmol/L	>500 mg/dL - 1000 mg/dL; >5.7 mmol/L - 11.4 mmol/L	>1000 mg/dL; >11.4 mmol/L
Urinary protein		Proteinuria	1+ proteinuria; urinary protein <1.0 g/24 hrs	2+ proteinuria; urinary protein 1.0 - 3.4g/24hrs	urinary protein >= 3.5g/24hrs	~

Document: [REDACTED]

Author: [REDACTED]

Template No.: [REDACTED]

Effective Date: 02Dec2019

Version Number: 2.5

Version Date: 18Feb2022

Reference: CS_WI_BS005

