## 5.3 Concomitant and Excluded Therapies

### 5.3.1 Concomitant Therapies

Concomitant therapy includes any prescription medications or over-the-counter preparations used by a patient between the 7 days preceding the screening evaluation and the termination visit. All concomitant medications should be reported to the investigator and recorded on the appropriate CRF.

Patients who use hormonal therapy with GnRH agonists for prostate cancer, oral contraceptives, hormone-replacement therapy, or other allowed maintenance therapy should continue their use.

Prophylactic use of anticoagulation for the maintenance of patency of permanent indwelling central venous access devices or for patients at high risk of venous thromboembolism is permitted during study treatment. If patients are receiving anticoagulation, they should be very closely monitored for potential haemorrhage, and:

- Patients who are receiving warfarin or Coumadin-like products should have their INR monitored and maintained at the lower third of the therapeutic range (ie, 2.0-2.3), unless a higher INR is required for anti-thrombotic efficacy.
- Patients who require low-molecular-weight heparin should receive the prophylactic dose and monitoring as specified by the appropriate product information label.

The investigator should closely monitor patients receiving anti-platelet and/or anti-thrombotic drugs with INR, aPTT and platelet count during study drug treatment and make a timely decision on whether to continue or stop such drugs in patients that report Grade  $\geq 2$  haemorrhagic events at any site, based on an individual assessment of the risk-benefit balance (See [Appendix J](#) for additional information on the clinical management of severe or serious haemorrhagic AEs).

Patients that develop arterial thromboembolic events should discontinue the study drug. If a patient suffers a venous thromboembolic event while still receiving study drug, it may still be possible for him or her to remain on study treatment under close monitoring and dose modification of study drug.

All supportive measures consistent with optimal patient care will be given throughout the study.

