17.4. LABORATORY EVALUATIONS

Results from the local laboratory will be included in the reporting of this study for Hematology, Serum chemistry, Coagulation, Urinalysis, 24-hours urine protein, and Thyroid function test.

Document: [REDACTED]

Author: [REDACTED]

Version Number:

2.5

Version Date:

18Feb2022

Template No.: [REDACTED]

Reference: CS_WI_BS005

Effective Date: 02Dec2019

Indexes collected for laboratory assessments are shown in table below:

Laboratory Test	Parameters
Hematology	red blood cell [RBC] count, hemoglobin, platelet count, white blood cell [WBC], neutrophils, lymphocytes, monocytes, eosinophils, basophils, hematocrit, reticulocyte count
Coagulation	activated partial thromboplastin time [aPTT], international normalized ratio [INR]
Serum chemistry	total protein, albumin, glucose, blood urea nitrogen [BUN], creatinine, creatinine clearance, alkaline phosphatase [ALP], lactate dehydrogenase [LDH], total bilirubin, Aspartate Aminotransferase [AST], Alanine Aminotransferase [ALT], calcium, magnesium, potassium, sodium, chloride, total cholesterol, triglycerides, uric acid, bicarbonate, phosphorus
Urinalysis	pH, glucose, protein, and blood
Thyroid function	thyroid stimulating hormone [TSH], free T3, and free T4

The non-protocol specified tests and urinalysis results will not be summarized; they will only be included in listings. Data recorded by the laboratory will be converted to the International System of Units (SI) and all presentations will use SI units. Quantitative laboratory measurements reported as “< X”, i.e., below the lower limit of quantification (LLQ), or “> X”, i.e., above the upper limit of quantification (ULQ), will be converted to X for the purpose of quantitative summaries, but will be presented as recorded, i.e., as “< X” or “> X” in the listings. Quantitative data collected between after date of ICF and up to 37 days following the last dose of study medication will be used for analysis. The following summaries will be provided for laboratory data:

- Observed value and change from baseline by visit (for quantitative measurements)
- Shift from baseline to worst post-baseline CTCAE toxicity for laboratory abnormalities
- Shift from baseline to the worst post-baseline investigators’ assessment (i.e., normal, abnormal but not clinically significant [NCS], abnormal and clinically significant [CS] for quantitative measurements and categorical measurements)

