17.4.1. LABORATORY SPECIFIC DERIVATIONS

The SI unit conversion and CTCAE grade will be derived through programming.

Document: [REDACTED]

Author: [REDACTED]

Version Number:

2.5

Version Date:

18Feb2022

Template No.: [REDACTED]

Reference: CS_WI_BS005

Effective Date: 02Dec2019

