17.4.2. CTCAE GRADING FOR LABORATORY DATA

To identify laboratory values of potential clinical importance, laboratory results will be graded according to NCI CTCAE Ver. 4.03, where applicable ([APPENDIX 6](#)). All grading will be based on laboratory values (being direct or some derived, corrected values) only, regardless of its interventional or symptomatic consequences.

Some modifications to the grading system will be applied:

- Grade 5 refers to fatal outcomes, which cannot be determined solely by laboratory values, therefore will not appear in the grading system.
- A further category denoted Grade 0 would include all laboratory values within normal range except missing values.
- Missing results shall be graded as missing.
- For some specific parameters with CTCAE grading in both high and low direction (e.g., calcium, glucose, magnesium, potassium, sodium), CTCAE in hyper and hypo directions will be presented separately, i.e., hyper for higher values of concern and hypo for lower values of concern.

Any graded abnormality that occurs following the initiation of study drug and represents at least a 1-grade change (i.e. increase or decrease) from the baseline assessment is defined as treatment emergent. The treatment-emergent laboratory abnormality defined by CTCAE will be summarized by CTCAE term, CTCAE toxicity grade, and visit. Any occurrence of grade 3 or grade 4 laboratory abnormality during the treatment period will also be summarized by visit.

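### INR is graded on fixed values with no anticoagulation rule, so INR raised on purpose during the study is tabulated as a Grade 2 or 3 abnormality; the SAP also leaves open whether calcium is albumin-corrected

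*SAP*

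**What the plan says.** **INR**

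- SAP Appendix 6, row "INR increased": Grade 1 is above 1.2 to 1.5, Grade 2 above 1.5 to 2.5 and Grade 3 above 2.5; there is no Grade 4. The row mentions neither baseline nor anticoagulants. Two other rows in the same appendix, creatinine and increased hemoglobin, do refer to baseline. aPTT is graded on multiples of the upper limit of normal, also without an anticoagulation clause.
- SAP 17.4.2: "All grading will be based on laboratory values (being direct or some derived, corrected values) only, regardless of its interventional or symptomatic consequences". A graded abnormality after the start of study drug is treatment-emergent if it differs from baseline by at least one grade. Any Grade 3 or 4 value in the treatment period is also summarized by visit, with no condition on baseline.
- SAP 17.4 plans two shift tables: one from baseline to worst CTCAE grade, and one from baseline to worst investigator assessment (normal, abnormal not clinically significant, abnormal clinically significant).
- Protocol 5.3.1: patients on warfarin-type products "should have their INR monitored and maintained at the lower third of the therapeutic range (ie, 2.0-2.3", with an allowance for a higher INR where anti-thrombotic efficacy needs it. Exclusion criterion 9 lifts its INR and aPTT limits for patients who take, or intend to take, prophylactic anticoagulants.

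**Calcium**

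- SAP Appendix 6 grades "Serum Calcium (mmol/L", with Grade 1 hypocalcemia at "<LLN - 2.0 mmol/L".
- SAP 17.4.1 lists the laboratory derivations in one sentence: "The SI unit conversion and CTCAE grade will be derived through programming". It gives no albumin correction.
- Albumin is collected in the same chemistry panel (SAP 17.4) and is graded in its own right.

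**The concern.** The protocol foresees patients whose INR is deliberately raised, and the SAP grades that INR as it would grade an unexplained rise. The laboratory tables are descriptive and have no control arm, so a reader cannot subtract a background rate of anticoagulant use. A treatment-emergent or Grade 3 line for INR would be read next to hemorrhage and hepatic dysfunction, which are both adverse events of special interest for this drug. Laboratory results are a named secondary safety endpoint of the expansion phase.

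For calcium, part of the measured total is bound to albumin. If the reported value is graded uncorrected, a fall in albumin can register both as hypoalbuminemia and as hypocalcemia, and true hypercalcemia can be understated when albumin is low. Proteinuria is an identified risk (52.1% in Protocol Table 3), so a fall in albumin on treatment is plausible, although that table lists neither hypoalbuminemia nor hypocalcemia.

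**Working it through.** **INR.** The inputs are the Appendix 6 bands, the Protocol 5.3.1 target of 2.0-2.3, and the one-grade rule in SAP 17.4.2. The plan gives no figure of its own to reproduce. Grading INR with the Appendix 6 bands gives 1.0 and 1.2 as Grade 0; 1.5 as Grade 1; 2.0, 2.1, 2.3 and 2.5 as Grade 2; and 2.6 and 3.0 as Grade 3. The whole target range therefore lies inside Grade 2.

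Applying the one-grade rule to pairs of values:

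| Baseline INR | On-study INR | Grades | Treatment-emergent? |
|---|---|---|---|
| 1.0 or 1.2 | 2.0-2.3 | 0 to 2 | yes |
| 1.5 | 2.0-2.3 | 1 to 2 | yes |
| 2.0 or 2.3 | 2.0-2.3 | 2 to 2 | no |
| 2.0 or 2.3 | 2.6 | 2 to 3 | yes, and in the Grade 3-4 summary |

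The miscount therefore falls on patients who start or intensify anticoagulation on study. The Grade 3-4 summary has no baseline condition, so a patient held above 2.5 throughout is also counted there, at each visit tested.

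Would grading relative to baseline solve it? Assume multipliers equal to the present cut-points, 1.5 and 2.5. A patient who stays within 2.0-2.3 has ratios from 2.0/2.3 = 0.87 to 2.3/2.0 = 1.15 and is no longer graded. A patient who goes from 1.0 to 2.0-2.3 has ratios of 2.0 to 2.3 and is still Grade 2. Baseline-relative grading therefore helps the patients who were already not treatment-emergent and misses those who start on study.

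**Calcium.** The documents give no correction formula, lower limit of normal (LLN) or albumin distribution, so everything here is an assumption. Take corrected calcium = reported calcium + 0.02 × (40 − albumin in g/L), with LLN from 2.10 to 2.20 mmol/L.

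- Reported 1.95 at albumin 30: 1.95 + 0.02 × 10 = 2.15. Grade 2 becomes Grade 0 (LLN 2.10 or 2.15) or Grade 1 (LLN 2.20).
- Reported 1.70 at albumin 30: 1.90. Grade 3 becomes Grade 2.

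For a range, assume in addition that corrected calcium has mean 2.35 and SD 0.09, and that albumin has SD 5 g/L. Reported calcium then has SD √(0.09² + (0.02 × 5)²) = 0.135. With LLN from 2.10 to 2.15, corrected calcium is below LLN in 0.3% to 1.3% of single draws.

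| Mean albumin (g/L) | Reported below LLN | Below 2.0 (Grade 2 or worse) | Below 1.75 (Grade 3 or worse) |
|---|---|---|---|
| 40 | 3% to 7% | 0.5% | 0.0004% |
| 37 | 8% to 15% | 1.6% | 0.003% |
| 34 | 17% to 28% | 4.4% | 0.018% |

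Under these assumptions the effect is confined almost entirely to Grades 1 and 2. The figures are single-draw prevalences and do not estimate treatment-emergent counts, because low albumin at baseline raises both sides of the comparison.

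**The case against.** **Not every anticoagulated patient is miscounted.** A reader might infer from exclusion criterion 9 that each patient admitted on an anticoagulant becomes a treatment-emergent case. The one-grade rule prevents that for anyone at target both at baseline and afterwards. This stands, and it limits the point to patients who start or intensify on study, to values above 2.5, and to the plain display of Grade 2 in the shift table.

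**A laboratory grade is not an attribution to the drug.** Section 17.4.2 grades values for potential clinical importance. Protocol 7.1.8.4 sets separate criteria for calling a laboratory value an adverse event, and the investigator judges relatedness. The adverse events of special interest are built from coded adverse event terms, so graded INR values do not feed the hemorrhage category. This also stands. The second shift table lets an investigator mark an expected INR as not clinically significant, which mitigates the problem in part. It does not correct the treatment-emergent and Grade 3-4 tables, which have no such filter.

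**The calcium text is open.** A reader might infer that the SAP grades total calcium uncorrected and so counts low albumin as hypocalcemia. The documents do not establish this. The row says neither total nor uncorrected, and 17.4.2 allows for some corrected values. What can be said is that no parameter is named and no formula is given, so a programmer following the text literally would grade the reported value.

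**Separating the values could hide over-anticoagulation.** This is a fair warning, and the remedy must guard against it.

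**Conclusion.** The INR point holds on the text. Appendix 6 states a rule that places the protocol's entire INR target in Grade 2 and any permitted value above 2.5 in Grade 3, and nothing else in the SAP adjusts for anticoagulation. The size within a patient is certain: a rise from 1.0-1.5 to 2.0-2.3 is treatment-emergent Grade 2. The size in the tables is unknown, because the documents do not say how many patients take warfarin-type drugs.

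The calcium point is secondary and conditional. It is a gap in specification that becomes an error only if the row is programmed as it reads. The percentages above rest wholly on assumed inputs and should not be presented as trial figures. They give no support for a claim that Grade 3-4 hypocalcemia would be materially inflated.

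Both points concern descriptive safety tables. The primary endpoint is untouched, and so is the definition of dose-limiting toxicity. Nothing here bears on what the INR target should be.

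**What to change.** **INR and aPTT (SAP 17.4.2 and Appendix 6).** Keep the bands. Add a flag for each INR and aPTT value taken while the patient was on an anticoagulant, from the concomitant medication dates and a pre-specified drug list. Class each post-baseline value by status on the day of sampling. Present the treatment-emergent, Grade 3-4 and shift tables separately for on- and off-anticoagulant values. Make the on-anticoagulant tables mandatory so that over-anticoagulation stays visible. Do not rely on baseline-relative grading alone.

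**Calcium (SAP 17.4.1 and Appendix 6).** State that calcium is graded on the albumin-corrected value. Give the formula, for example reported calcium + 0.02 × (40 − albumin in g/L) with same-day albumin, relabel the row accordingly, and list measured calcium. In 17.4.2, name any other parameter to which the reference to corrected values applies.

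**Cost.** SAP wording, one flag and one derived variable, all from data already collected, plus a small amount of extra tabulation. Calcium would be ungraded where same-day albumin is missing. No study procedure changes.
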